12 APPENDICES

Appendix 1 Sponsor's Grading for Laboratory Values

Sponsor's Grading for Laboratory Values

	Grade 1	Grade 2	Grade 3	Grade 4
BLOOD/BONE MARROW				
Hemoglobin	<LLN – 10.0 g/dL <LLN – 100 g/L <LLN – 6.2 mmol/L	<10.0 – 8.0 g/dL <100 – 80 g/L <6.2 – 4.9 mmol/L	<8.0 g/dL <80 g/L <4.9 mmol/L; transfusion indicated	life-threatening consequences; urgent intervention indicated
Leukocytes (total WBC)	<LLN – 3.0×10 ⁹ /L <LLN – 3000/mm ³	<3.0 – 2.0×10 ⁹ /L <3000 – 2000/mm ³	<2.0 – 1.0×10 ⁹ /L <2000 – 1000/mm ³	<1.0×10 ⁹ /L <1000/mm ³
Lymphocytes	<LLN – 800/mm ³ <LLN – 0.8×10 ⁹ /L	<800 – 500/mm ³ <0.8 – 0.5×10 ⁹ /L	<500 – 200/mm ³ <0.5 – 0.2×10 ⁹ /L	<200/mm ³ <0.2×10 ⁹ /L
Neutrophils	<LLN – 1.5×10 ⁹ /L <LLN – 1500/mm ³	<1.5 – 1.0×10 ⁹ /L <1500 – 1000/mm ³	<1.0 – 0.5×10 ⁹ /L <1000 – 500/mm ³	<0.5×10 ⁹ /L <500/mm ³
Platelets	<LLN – 75.0×10 ⁹ /L <LLN – 75,000/mm ³	<75.0 – 50.0×10 ⁹ /L <75,000 – 50,000/mm ³	<50.0 – 25.0×10 ⁹ /L <50,000 – 25,000/mm ³	<25.0×10 ⁹ /L <25,000/mm ³
METABOLIC/LABORATORY				
Albumin, serum- low (hypoalbuminemia)	<LLN – 3 g/dL <LLN – 30 g/L	<3 – 2 g/dL <30 – 20 g/L	<2 g/dL <20 g/L	life-threatening consequences; urgent intervention indicated
Alkaline phosphatase	>ULN – 3.0×ULN	>3.0 – 5.0×ULN	>5.0 – 20.0×ULN	>20.0×ULN
ALT	>ULN – 3.0×ULN	>3.0 – 5.0×ULN	>5.0 – 20.0×ULN	>20.0×ULN
AST	>ULN – 3.0×ULN	>3.0 – 5.0×ULN	>5.0 – 20.0×ULN	>20.0×ULN
Bilirubin (hyperbilirubinemia)	>ULN – 1.5×ULN	>1.5 – 3.0×ULN	>3.0 – 10.0×ULN	>10.0×ULN
Calcium, serum-low (hypocalcemia)	<LLN – 8.0 mg/dL <LLN – 2.0 mmol/L	<8.0 – 7.0 mg/dL <2.0 – 1.75 mmol/L	<7.0 – 6.0 mg/dL <1.75 – 1.5 mmol/L	<6.0 mg/dL <1.5 mmol/L
Calcium, serum-high (hypercalcemia)	>ULN – 11.5 mg/dL >ULN – 2.9 mmol/L	>11.5 – 12.5 mg/dL >2.9 – 3.1 mmol/L	>12.5 – 13.5 mg/dL >3.1 – 3.4 mmol/L	>13.5 mg/dL >3.4 mmol/L
Cholesterol, serum-high (hypercholesterolemia)	>ULN – 300 mg/dL >ULN – 7.75 mmol/L	>300 – 400 mg/dL >7.75 – 10.34 mmol/L	>400 – 500 mg/dL >10.34 – 12.92 mmol/L	>500 mg/dL >12.92 mmol/L
Creatinine	>ULN – 1.5×ULN	>1.5 – 3.0×ULN	>3.0 – 6.0×ULN	>6.0×ULN
GGT (γ-glutamyl transpeptidase)	>ULN – 3.0×ULN	>3.0 – 5.0×ULN	>5.0 – 20.0×ULN	>20.0×ULN
Glucose, serum-high (hyperglycemia)	Fasting glucose value: >ULN – 160 mg/dL >ULN – 8.9 mmol/L	Fasting glucose value: >160 – 250 mg/dL >8.9 – 13.9 mmol/L	>250 – 500 mg/dL; >13.9 – 27.8 mmol/L; hospitalization indicated	>500 mg/dL; >27.8 mmol/L; life-threatening consequences
Glucose, serum-low (hypoglycemia)	<LLN – 55 mg/dL <LLN – 3.0 mmol/L	<55 – 40 mg/dL <3.0 – 2.2 mmol/L	<40 – 30 mg/dL <2.2 – 1.7 mmol/L	<30 mg/dL <1.7 mmol/L life-threatening consequences; seizures

Sponsor's Grading for Laboratory Values

	Grade 1	Grade 2	Grade 3	Grade 4
Phosphate, serum-low (hypophosphatemia)	<LLN – 2.5 mg/dL <LLN – 0.8 mmol/L	<2.5 – 2.0 mg/dL <0.8 – 0.6 mmol/L	<2.0 – 1.0 mg/dL <0.6 – 0.3 mmol/L	<1.0 mg/dL <0.3 mmol/L life-threatening consequences
Potassium, serum-high (hyperkalemia)	>ULN – 5.5 mmol/L	>5.5 – 6.0 mmol/L	>6.0 – 7.0 mmol/L hospitalization indicated	>7.0 mmol/L life-threatening consequences
Potassium, serum-low (hypokalemia)	<LLN – 3.0 mmol/L	<LLN – 3.0 mmol/L; symptomatic; intervention indicated	<3.0 – 2.5 mmol/L hospitalization indicated	<2.5 mmol/L life-threatening consequences
Sodium, serum-high (hypernatremia)	>ULN – 150 mmol/L	>150 – 155 mmol/L	>155 – 160 mmol/L hospitalization indicated	>160 mmol/L life-threatening consequences
Sodium, serum-low (hyponatremia)	<LLN – 130 mmol/L	N/A	<130 – 120 mmol/L	<120 mmol/L life-threatening consequences
Triglyceride, serum-high (hypertriglyceridemia)	150 – 300 mg/dL 1.71 – 3.42 mmol/L	>300 – 500 mg/dL >3.42 – 5.7 mmol/L	>500 – 1000 mg/dL >5.7 – 11.4 mmol/L	>1000 mg/dL >11.4 mmol/L life-threatening consequences
Uric acid, serum-high (hyperuricemia)	>ULN – 10 mg/dL ≤0.59 mmol/L without physiologic consequences	N/A	>ULN – 10 mg/dL ≤0.59 mmol/L with physiologic consequences	>10 mg/dL >0.59 mmol/L life-threatening consequences

ALT = alanine aminotransferase (serum glutamic pyruvic transaminase), AST = aspartate aminotransferase (serum glutamic oxaloacetic transaminase), GGT = γ -glutamyl transpeptidase, N/A = not applicable, LLN = lower limit of normal, ULN = upper limit of normal, WBC = white blood cell.

Based on Common Terminology Criteria for Adverse events (CTCAE) Version 4.0. Published: May 28, 2009 (v4.03: June 14, 2010).

2 LIST OF ABBREVIATIONS AND DEFINITIONS OF TERMS

Abbreviation	Term
AE	adverse event
AED	antiepileptic drug
ATC	anatomical therapeutic class
BMI	Body Mass Index
BP	blood pressure
CI	confidence interval
CRF	case report form
C-SSRS	Columbia-Suicide Severity Rating Scale
ECG	electrocardiogram
EEG-IPS	electroencephalogram intermittent photic stimulation
EOT	end of treatment
LNH	low/normal/high
LS	least square
MedDRA	Medical Dictionary for Regulatory Activities
PD	pharmacodynamic(s)
CCI	
PK	pharmacokinetic(s)
PPR	photoparoxysmal response
PT	preferred term
SAE	serious adverse event
SAP	statistical analysis plan
SAS	Statistical Analysis System
SD	standard deviation
SI	Système International
SOC	system organ class
TEAE	treatment-emergent adverse event
TLG	tables, listings, and graphs
WHO DD	World Health Organization drug dictionary

3 INTRODUCTION

The purpose of this statistical analysis plan (SAP) is to describe the procedures and the statistical methods that will be used to analyze and report results for Eisai Protocol E2730-A001-201.

3.1 Study Objectives

3.1.1 Primary Objective

The primary objective of the study is to assess the pharmacodynamics (PD) activity of E2730 as measured by suppression of epileptic PPR in the subject's most sensitive eye condition as a proof of principle of efficacy in subjects with photosensitive epilepsy.

[figure not shown]
3.1.2 Secondary Objectives

The secondary objectives of the study are:

- To assess the PD activity of E2730 as measured by suppression of epileptic PPR, onset, maximum change, and duration of response in 3 eye-conditions (eye closure, eyes closed, and eyes open) in subjects with photosensitive epilepsy.
- To assess the safety and tolerability of E2730 following a single oral dose in subjects with photosensitive epilepsy.
- To assess the pharmacokinetics (PK) of E2730 following a single oral dose in subjects with photosensitive epilepsy.
- To evaluate potential exposure-PD response relationships.

3.1.3 CCI

CCI

3.2 Overall Study Design and Plan

This is a multicenter, double-blind, randomized, 6-sequence, 3-treatment, 3-period cross-over study in adult subjects with epilepsy. This study will use the photosensitivity proof of principle model to determine the potential of E2730 to reduce the photosensitive range in adult subjects. This study will have 2 phases: Prerandomization and Randomization. The Prerandomization Phase will consist of a Screening Period (up to 3 weeks), during which each subject's study eligibility will be determined and baseline assessments will be conducted. The Randomization Phase will consist of 3 Treatment Periods with a single dose in each period (placebo, E2730 40 mg, or E2730 120 mg, each separated by a 3-week (± 3 days) washout interval for a total of approximately 6 weeks), and a Follow-up Period (a

single visit, 3 weeks ± 3 days after the last day of study product administration). All visits will be conducted on an outpatient basis. Each subject will receive a single oral dose in a cross-over sequence according to his/her randomization code for the treatment sequence.

[figure not shown]
Table of Treatment Sequences

Sequence	Treatment Period 1	Treatment Period 2	Treatment Period 3
1: ABC	Placebo	E2730 40 mg	E2730 120 mg
2: BCA	E2730 40 mg	E2730 120 mg	Placebo
3: CAB	E2730 120 mg	Placebo	E2730 40 mg
4: ACB	Placebo	E2730 120 mg	E2730 40 mg
5: BAC	E2730 40 mg	Placebo	E2730 120 mg
6: CBA	E2730 120 mg	E2730 40 mg	Placebo

A = Placebo; B = E2730 40 mg; C = E2730 120 mg

An overview of the study design is presented by [Figure 1](#) in the study protocol as follows.

Figure of Study Design for a Crossover Study

ED = Early discontinuation, FU = Follow Up, Pd = period, R = randomization, Trt = treatment, WO = washout.

4 DETERMINATION OF SAMPLE SIZE

Approximately 9 subjects with photosensitive epilepsy and a stable PPR will be needed to be randomized in the study in order to obtain 6 evaluable subjects. Based on a similar study in subjects with photosensitive epilepsy (NCT02564029), an estimated standard deviation of the treatment group difference of the SPR in the subject's most sensitive eye condition is 3.62. The width of a 90% CI of the mean group difference based on this standard deviation assumption and 6 subjects is 2.431. Therefore, a sample size of 6 would be sufficient to detect a mean group difference of 3 or larger with 90% confidence.

Subjects who discontinue from the study early may be replaced, after consultation with the sponsor. A subject will be defined as evaluable if the subject has completed at least 2 treatment periods (including one with placebo) and has more than 50% non-missing postdose PPR data in each period to get the average PPR value (ie, at least 3 of 5 posedge PPR data are valid in each period).

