9.7.1.1 Study Endpoints

The reduction in PPR response will be evaluated for 8 hours postdose for the entire time period. A diminution in response is anticipated with the dose range. A statistical difference of treatment doses versus placebo will be evaluated.

The primary endpoint, the change in the PPR range, is evaluated using mixed effects model for comparing low and high treatment doses versus placebo. Another endpoint will include proportions of subjects responding to treatment versus placebo. Most patients have strong responses to effective treatments compared to placebo, which can be evaluated by graphs of partial response (ie, 3 steps narrowing) and abolition of PPR.

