9.7.2 Determination of Sample Size

Approximately 9 subjects with photosensitive epilepsy and a stable PPR will be needed to be randomized in the study in order to obtain 6 evaluable subjects. Based on a similar study in subjects with photosensitive epilepsy (NCT02564029), an estimated standard deviation of the treatment group difference of the SPR in the subject's most sensitive eye condition is 3.62. The width of a 90% CI of the mean group difference based on this standard deviation assumption and 6 subjects is 2.431. Therefore, a sample size of 6 would be sufficient to detect a mean group difference of 3 or larger with 90% confidence.

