5.3.5 Handling of Missing Data, Dropouts, and Outliers

If there are more than 3 dropouts in the study, a subject discontinuing/discontinued from the study for any reason may be replaced at the discretion of the sponsor. Missing values in PPR will not be imputed in this study.

For PD analyses, two summaries for the primary and secondary PPR endpoints will be produced, if different, one for all data in PD analysis set and one for all completers.

For safety summaries, all data in Safety Analysis Set will be included.

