5.5.2 Pharmacodynamic Analyses

The following PD analyses will be performed on the PD Analysis Set.

No multiplicity adjustments will be made. The 5 PPR measured postdose on a treatment day will be averaged and used for both primary endpoint and secondary endpoints. The predose PPR data from the respective treatment period will be used as the baseline data for that period.

Primary PD Analyses

The primary endpoint of mean change from baseline of the average PPR for each E2730 dose compared with placebo in the most sensitive eye condition will be performed using a mixed effects model for crossover study. The model will include treatment, period, and sequence as fixed effects, baseline (predose) measurement as a covariate, and subject nested within sequence as a random effect. Where data are normally distributed, least squares (LS) means, difference in LS means of each E2730 dose compared to placebo, and 90% CIs will be presented with no adjustments for multiplicity.

Secondary PD Analyses

The secondary endpoints of mean change from baseline of the average PPR for each E2730 dose compared with placebo in all 3 different eye conditions (eye closure, eyes closed, and eyes open) will be analyzed and summarized by using the same mixed effects model as for primary PD analyses.

Additional analysis by graphical exploration on onset, maximum change, and duration of photosensitivity response at each dose level will be performed for all 3 eye conditions at the time course of E2730 as compared to placebo. This analysis will provide further information on the frequency and percentage of subjects with Complete Suppression, Partial Response, and No Response of PPR (see [Section 8.3 Definitions of Derived PPR Variables](#)) at each dose level of E2730 as compared to placebo.

Sensitivity analyses for PPR may be conducted, for example, of PPR for subjects who completed all Treatment Periods 1-3 versus those who are included in the PD Analysis Set.

CCI

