13.2 SAS Code of Mixed Model for Primary PD Analyses

```

proc mixed data= xxxx;
  class USUBJID TRTPN PERIOD SEQUENCE ;
  model AVAL = TRTPN PERIOD SEQUENCE BASE /SOLUTION ddfm= kr;
  random USUBJID(SEQUENCE) ;
  lsmeans TRTPN/alpha= 0.1 PDIFF CL ;
run;

```

SIGNATURE PAGE

Author:

[electronic signature in eDMS]

PPD

Date

Neurology Business Group

Approval:

[electronic signature in eDMS]

PPD

Date

Neurology Business Group

[electronic signature in eDMS]

PPD

Date

Neurology Business Group

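### The 2.431 given as the width of the 90% CI is its normal-approximation half-width; the planned t-based half-width is about 2.8 to 3.0, and 'detecting' a difference of 3 holds only for an observed difference

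*SAP*

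**What the plan says.** The same rationale stands in the protocol synopsis, protocol 9.7.2 and SAP section 4. About 9 subjects are randomized to obtain 6 evaluable ones. From a similar earlier study it takes an SD of 3.62 for the treatment difference in SPR in the most sensitive eye condition. It then says "The width of a 90% CI of the mean group difference based on this standard deviation assumption and 6 subjects is 2.431", and concludes that "a sample size of 6 would be sufficient to detect a mean group difference of 3 or larger with 90% confidence". No power is stated.

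SAP 5.5.2 plans a crossover mixed model, with the "difference in LS means of each E2730 dose compared to placebo, and 90% CIs will be presented with no adjustments for multiplicity". The code in SAP 13.2 has "model AVAL = TRTPN PERIOD SEQUENCE BASE /SOLUTION ddfm= kr" and "lsmeans TRTPN/alpha= 0.1 PDIFF CL", that is, two-sided 90% limits with Kenward-Roger degrees of freedom. Protocol 9.7.1.1 adds: "A statistical difference of treatment doses versus placebo will be evaluated".

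SAP section 4 also defines who counts towards the six: "A subject will be defined as evaluable if the subject has completed at least 2 treatment periods (including one with placebo"), with at least 3 of the 5 postdose values valid in each period. On replacement, SAP section 4 allows it after consultation with the sponsor. SAP 5.3.5 says that, with more than 3 dropouts, "a subject discontinuing/discontinued from the study for any reason may be replaced at the discretion of the sponsor".

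**The concern.** The width of an interval is the distance between its two limits. The stated inputs give 2.431 only as the distance from the estimate to one limit, and only if the SD is treated as known. So the label is wrong by a factor of two, and the multiplier is not the one the planned analysis will use.

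The sentence that follows places the word *detect* beside a confidence level. A confidence level of 90% is not a 90% chance of finding an effect, yet the sentence can be read that way, more so because the protocol says a statistical difference from placebo will be evaluated.

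This is the only numerical justification of the trial's size in the documents. Someone relying on it could expect a 3-unit effect to be shown reliably with six subjects, and could over-read a result whose interval includes zero. Three units is also the SAP's own threshold for suppression and partial response (SAP 8.3), so the misreading would concern an effect size the plan treats as relevant.

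**Working it through.** **Inputs.** SD of the treatment difference 3.62, n = 6 and difference 3 (SAP section 4); two-sided 90% limits on t with Kenward-Roger df (SAP 13.2).

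**Assumptions.** 3.62 is the SD of the within-subject dose-minus-placebo difference (the reading that reproduces the plan's figure), and it is unchanged by baseline adjustment. The df run from 5 (paired analysis, 6 − 1) to 7 (planned model with one completer per sequence: 18 observations − 6 subjects − 2 periods − 2 treatments − 1 baseline).

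**1. The plan's figure.**
- SE = 3.62/√6 = 1.4779.
- 1.6449 × 1.4779 = 2.431. This is the half-width; the full width is 2 × 2.431 = 4.86.
- A full width of 2.431 would need n = (2 × 1.6449 × 3.62/2.431)² ≈ 24.

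**2. On the t basis, n = 6.**

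| df | t(0.95) | Half-width | Full width | Shortfall of 2.431 |
|---|---|---|---|---|
| 7 | 1.8946 | 2.80 | 5.60 | 13% |
| 5 | 2.0150 | 2.98 | 5.96 | 18% |

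An observed difference of 3 exceeds the half-width on every one of these bases, by 0.57 (normal), 0.20 (7 df) or 0.02 (5 df).

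**3. If the true difference is 3.** Probability that the 90% CI excludes zero in the right direction, from the noncentral t with noncentrality 3/SE:
- n = 6: noncentrality 3/1.4779 = 2.03; 54% (5 df) to 57% (7 df).
- n = 9, all contributing and treatments balanced over periods: SE = 3.62/3 = 1.2067, noncentrality 2.49; 73% (8 df, paired) to 76% (13 df, model: 27 − 9 − 2 − 2 − 1).

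**4. What the evaluability rule allows.** A subject with placebo and one dose counts as evaluable, so six evaluable subjects need not give six pairs for each dose. Take one subject per sequence, with one subject missing one dose. Least squares with subject, period and treatment effects, residual SD 3.62/√2 and one df for baseline leaves 17 − 6 − 2 − 2 − 1 = 6 df, t(0.95) = 1.9432:
- Affected dose: SE 1.610, half-width 1.9432 × 1.610 = 3.13, above 3.
- Other dose: SE 1.478, half-width 2.87.

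**5. Balance.** An illustrative set of six completers with uneven sequences (two ABC, two ACB, one BCA, one CAB) gives SE 1.657 and, at 7 df, a half-width of 1.8946 × 1.657 = 3.14. The example is chosen to show the direction; its likelihood cannot be judged from the documents.

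**The case against.** The fair defence is that the sponsor meant a half-width. Setting 3 against 2.431 makes sense only that way, and with six balanced completers 3 still exceeds even the strictest half-width, 2.98. Sizing a small proof-of-principle study on CI precision is legitimate. The plan sets no power target and no success rule, so a detection probability applies a standard it never adopted. The PD Analysis Set takes in every randomized, dosed subject with enough data, so more than six may contribute, and replacement is possible.

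Most of this stands, and it limits the point. A reader might infer that the rationale is unqualified; it is not, because it states the SD, the six subjects and the confidence level. A reader might also infer that the threshold of 3 is overturned; it is not, under complete and balanced data.

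What the defence does not remove is that the figure is mislabelled in three places, that its multiplier is not the planned one, and that *detect* invites a reading about a true difference which the calculation does not support. Stating the probability at a true difference of 3 clarifies that word; it does not impose a power requirement. Replacement is discretionary and does not secure six pairs for each dose.

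**Conclusion.** The point holds as an error of statement. The value 2.431 is a half-width on the normal approximation. The full width is 4.86 on that basis, and 5.6 to 6.0 on the planned t basis, where the half-width is 2.8 to 3.0. The conclusion about a difference of 3 is true of an observed difference with six complete subjects balanced over sequences, and by a small margin. One missed dose among the six takes the half-width for that dose to about 3.1.

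A reader might go further and conclude that the trial is too small or its analysis flawed. The documents do not support that: no power was promised, and the planned model will report t-based intervals whatever the rationale says.

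The figures rest on 3.62 being a within-subject SD that carries over to the baseline-adjusted model, which the documents do not let one test, and on the 5 to 7 df range. Kenward-Roger df will vary with the data pattern; 8 df would give a half-width of 2.75, which changes nothing of substance. The arithmetic is certain. The correction is worth making because nothing else in the documents justifies the sample size numerically.

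**What to change.** In the protocol synopsis, protocol 9.7.2 and SAP section 4, replace the last two sentences of the rationale with:

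> Assuming an SD of 3.62 for the within-subject difference and 6 subjects completing all periods with balanced sequences, the half-width of the 90% CI is about 2.8–3.0 (t, 7 to 5 df; normal approximation 2.43; full width about 5.6–6.0), so an observed difference of 3 or larger would exclude zero. If the true difference is 3, the probability that the 90% CI excludes zero is about 54–57% with 6 subjects and about 73–76% if all 9 contribute. Because an evaluable subject may contribute to only one dose–placebo comparison, precision may be lower; for example, if one of the 6 subjects misses one dose, the half-width for that dose is about 3.1 under the planned model.

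This changes wording only. The evaluability definition, replacement rule, endpoint, model and number of subjects stay as they are. The cost is that the stated precision looks less favourable.

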5.2 Study Subjects

5.2.1 Definitions of Analysis Sets

The Safety Analysis Set is the group of subjects who receive at least 1 dose of study drug and have at least 1 postdose safety assessment.

The Pharmacokinetic Analysis Set is the group of randomized subjects who receive at least 1 dose of study drug and have sufficient PK data to derive at least 1 PK parameter.

The Pharmacodynamic Analysis Set is the group of randomized subjects who receive at least 1 dose of study drug and have sufficient PD data to derive at least 1 PD parameter.

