8.3 Definitions of Derived PPR Variables

The followings are definitions for PPR related analyses:

- Standard Photosensitivity Response (SPR): a standardized derived measure of the range of frequencies of IPS that elicits epileptiform EEG responses in a subject. The range is assigned a number, representing the number of frequency steps, from 0 to 14 between the lowest to the highest frequencies of IPS that elicits epileptiform activity by EEG. If the upper and lower limit of measured frequencies is the same, SPR will be set = 1.
- Most sensitive eye condition: SPR is measured in each of 3 eye states: eye closure, eyes closed, and eyes open. That eye condition that yields the largest SPR before dosing is defined as the most sensitive eye condition.
- Duration of suppression: The difference in hours between the onset of suppression and the end of suppression of photosensitivity. The onset of suppression is defined as the first time point at which the SPR was at least 3 units below the mean SPR at baseline. The end of suppression is defined as the last time (second time) with two successive reductions in SPR of at least 3 units lower than the mean SPR at baseline.
- Complete suppression is defined as a standardized photosensitivity response (SPR) reduction to 0 over at least 1 time point for all three eye conditions. Partial response is defined as a reduction in SPR of at least 3 units from baseline for at least 3 time points, and no time points with at least 3 units of increase, in the most sensitive eye condition; without meeting the complete suppression definition. No response is

defined as the response not meeting complete suppression or partial suppression definitions.

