9 PROGRAMMING SPECIFICATIONS

The rules for programming derivations and dataset specifications will be provided in separate documents.

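### Does the SAP leave open how many postdose readings the primary period average needs when photic stimulation is stopped early?

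*SAP*

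**What the plan says.** SAP 5.5.2 defines the period value: "The 5 PPR measured postdose on a treatment day will be averaged and used for both primary endpoint and secondary endpoints". It sets no minimum for a day with fewer readings. The only count is in SAP 4, where an evaluable subject has at least two periods, one of them placebo, and "has more than 50% non-missing postdose PPR data in each period to get the average PPR value", spelled out there as at least 3 of 5.

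The primary model uses the PD Analysis Set, not the evaluable subjects. Membership requires that subjects "have sufficient PD data to derive at least 1 PD parameter" (SAP 5.2.1). SAP 5.3.5 adds "Missing values in PPR will not be imputed in this study" and promises two sets of PPR summaries if they differ, "one for all data in PD analysis set and one for all completers". SAP 8.3 defines SPR, the most sensitive eye condition and the response categories, but not the period average, and the SAS code in SAP 13.2 takes the analysis value as given. SAP 9 says: "The rules for programming derivations and dataset specifications will be provided in separate documents".

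On conduct, criterion 3 in Protocol 9.3.3.1 ends photic stimulation for the day once the range has widened by more than 3 points against Screening on two consecutive postdose occasions. Readings are scheduled at 1, 2, 4, 6 and 8 hours.

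**The concern.** Two parts of the SAP describe the same average with different data requirements: five readings in one place, three of five in another. Short days are also not random. Criterion 3 produces them when a subject is doing badly, so a rule that discards a day with 2 of 5 readings discards it for a reason tied to its outcome.

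With about 9 randomised and 6 evaluable subjects, one period carries weight. Two programmers could follow the SAP text, choose different minimum counts and report different primary estimates from the same readings. A choice made after unblinding could be steered by the result. A placebo day stopped at 2 hours would also make the subject non-evaluable under SAP 4.

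**Working it through.** **Yardstick.** SAP 4 gives "an estimated standard deviation of the treatment group difference of the SPR" as 3.62, with 6 subjects and 90% confidence. The normal half-width is 1.645 × 3.62 / √6 = 2.431, which reproduces the stated figure. The SAP calls it a width; here it serves only as a scale.

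**Readings left after a stop under criterion 3**

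| Widened at | Readings kept | Share | At least 3 of 5? |
|---|---|---|---|
| 1 and 2 h | 2 of 5 | 40% | no |
| 2 and 4 h | 3 of 5 | 60% | yes |
| 4 and 6 h | 4 of 5 | 80% | yes |
| 6 and 8 h | 5 of 5 | 100% | yes |

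Only the first row separates 3-of-5 from averaging whatever was observed.

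**Is one rule better?** Assume 6 subjects, five 120 mg periods with a change of −3, and one 120 mg period at +4 at 1 and 2 h and then stopped. Call each of the three untested readings L. The full average for that period is (8 + 3L)/5. Keeping the two readings gives a 120 mg mean of (5 × −3 + 4)/6 = −1.83. Dropping the period gives −3.00.

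| L | Full-data mean | Error if kept | Error if dropped |
|---|---|---|---|
| +4 | −1.83 | 0 | 1.17 |
| 0 | −2.23 | 0.40 | 0.77 |
| −3 | −2.53 | 0.70 | 0.47 |

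The errors are equal when (8 + 3L)/5 = 0.5, the midpoint of +4 and −3, so L = (2.5 − 8)/3 = −1.83. Above that, keeping is closer; below it, dropping is. The documents do not say which is likelier.

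**Simulated size (assumed inputs).** 9 subjects; true effects 0, −1.5 and −3 for placebo, 40 mg and 120 mg; mean SPR 7; between-subject SD 1.5; reading SD 1; period-average variance 3.62²/2 = 6.55. The fit was within-subject least squares with treatment, period and baseline, not the SAP's mixed model. Mean 120 mg minus placebo:

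| Day-to-day variation | All 5 known | Observed mean | 3-of-5 | 5-of-5 |
|---|---|---|---|---|
| Shared with predose | −2.88 | −2.89 | −2.79 | −2.77 |
| Arising after dosing | −2.89 | −2.90 | −2.53 | −2.40 |
| After dosing, 1–2 h only | −2.94 | −3.15 | −2.78 | −2.78 |

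The largest 3-of-5 gap is 2.89 − 2.53 = 0.36, about 15% of 2.43. It pulls towards zero because stops fall mainly on placebo days when the drug works. With half the SD, all rules are within 0.06 of full data, small even against a halved half-width of about 1.22. With no drug effect they agree within 0.03 on average.

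**Stop rates behind those figures.** With the full SD, 8.6% to 15.5% of placebo periods stop at 1 and 2 h. The upper end arises when Screening is given its own independent day shift; without that, every split gives about 9%. With half the SD the range is 1.1% to 3.1%.

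**The case for a change.** The strongest case for a change is that the minimum count belongs to the definition of the primary variable and should be fixed before unblinding. The gap is real. SAP 5.5.2, 5.2.1, 5.3.5, 8.3 and 13.2 set no count, and barring imputation does not choose between averaging what exists, 3 of 5, or all 5. With the full SD, in trials that have a 1 and 2 h stop, the observed-mean and 3-of-5 estimates differ by 0.24 to 0.67 on average. One sentence would close the gap.

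The silence stands; the conflict does not. SAP 5.5.2 names the scheduled readings and SAP 4 says how many are needed to form their average. Requiring all five rests on a single phrase and sits badly with SAP 4, which accepts an average from three, so the most extreme estimate (−2.40) tests the least supported reading. SAP 9 places derivation rules in other documents, where a minimum count would normally sit.

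The effect on evaluability also stands, but it touches only the count towards 6. No planned analysis is restricted to evaluable subjects, 9 are randomised, and replacement is allowed.

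Nor would a stopped day be hidden. Protocol 9.7 describes the range at every time point by treatment, SAP 5.3 lists all subjects, and SAP 5.5.2 allows sensitivity analyses. SAP 8.3 states: "Partial response is defined as a reduction in SPR of at least 3 units from baseline for at least 3 time points". A day with two readings cannot meet that, and a widened range cannot be 0 in all three eye conditions, so the day counts as No response.

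**Conclusion.** No change is needed. The SAP text is silent on one derivation detail that analysts can fill sensibly: average the observed scheduled readings without imputation, with 3 of 5 as the natural minimum, applied alike to every cause of missing readings. The worked case shows that neither keeping nor dropping a two-reading day is always closer to the truth, so writing in one rule would correct no wrong result. A table of stops, or an estimate with and without stopped periods, would be an optional addition to summaries and listings already planned.

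The likely effect is small: at most 0.06 SPR units with half the planning SD and 0.03 on average with no drug effect, against 2.43. It is larger only if the whole 3.62 is day-to-day variation, an upper bound, since that SD may also contain differences in drug response and SAP 4 describes subjects with a stable PPR. In that case the 3-of-5 gap of up to 0.36 works against the drug on average, though a single trial could move either way. These sizes rest on assumed variances and stop rates that the documents do not give. The safety stopping rule is not in question.
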